examine cognitive function under a variable duration of LFS. We hypothesize that there will be a trend towards improvement in task performance under the LFS setting, measured through reaction time and error rates, and that this improvement will be stable or enhanced with sustained LFS. We hope to utilize these results to inform the design of a larger phase 2 efficacy study. Our specific aims are as follows:

- 1) To monitor the safety of LFS in the STN of patients with PD by examining the psychological, cognitive, and motor consequences of LFS
- 2) To determine the feasibility of utilizing low frequency DBS to improve cognition in patients with PD by examining if there is a trend toward improved executive function with LFS over high frequency stimulation (HFS) and no stimulation settings.
- 3) To further examine feasibility by determining if the differential effects of LFS versus HFS of the STN are long lasting in a small patient group.

At present, DBS stimulators are set at varying stimulation frequencies based on the acute effects of DBS on motor performance, with limited understanding of cognitive consequences. Understanding the effects of different stimulation frequencies on non- motor tasks will help elucidate the mechanism behind cognitive impairment in PD. If our hypotheses are correct it could lead to the development of new treatment plans that involve alternating between low and high frequency stimulator settings to optimize both motor and cognitive domains. Ultimately, focused treatment for cognition may slow the progression from mild cognitive impairment to dementia, improving real world functioning and quality of life.

5) Background

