Treatment for cognitive impairment remains limited. Only rivastigmine has received approval from the FDA for PDD but is only modestly effective (Emre et al 2004). The conventional Dopa Replacement Therapy (DRT) improves motor symptoms but shows mixed effects on cognitive symptoms, improving some, and worsening others, largely due to nonspecific increases in dopamine (Poletti & Bonuccelli 2013). Deep Brain Stimulation (DBS) allows for targeted treatment to specific areas of the BGn. Currently, high frequency stimulation (HFS) is performed in the STN or globus pallidus interna (GPi) and has proved very effective in reducing motor symptoms when DRT has lost efficacy (Volkman 2004), but like its oral counterpart, does not show substantial improvements in cognitive functioning (Halpern et al 2009). Some studies even show worsening function in verbal fluency and some executive function domains (Heo et al 2008). Unlike oral therapy, our understanding of how DBS works to improve BGn functioning remains in its infancy. There are great potentials for adjusting contact locations, stimulation frequency, and other stimulator settings in increasingly complex ways to optimize both motor and non-motor symptoms of PD. For example, the dorsal STN is thought to be more motor related and some propose that spread of current to non-motor regions of the STN may be responsible for cognitive impairments associated with STN DBS. In fact, controlling spread by computational modeling techniques to minimize ventral stimulation prevented some of the cognitive deficits observed with STN stimulation (Frankemolle et al 2010).

Clinical trials using DBS to improve cognition are underway with exciting preliminary reports. HFS of part of the hypothalamus improved cognition in 6 patients with mild Alzheimer's disease, increased activity in downstream circuitry involved in memory, and slowed cognitive decline (Laxton et al 2013, Laxton et al 2010).

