This study will not affect whether PD patients receive a stimulator as all subjects are scheduled to undergo stimulation placement as part of their routine care. It also will not disrupt the standard procedure for implantation or initiation of treatment. The study will be conducted only in the brief period prior to the time when the stimulator is typically turned on. FDA approval for PD treatment is not limited to a specific stimulation frequency, and stimulator parameters are typically adjusted as symptoms evolve over time. The effect of participating in this study will therefore be minimal.

Patient's stimulators are typically turned on 4 weeks following electrode placement surgery at UC Davis. We plan to perform frequency manipulation and cognitive testing 3 weeks following electrode placement surgery, and 2 weeks following the surgery for the Implantable Pulse Generator (IPG). The study will therefore be completed prior to the standard time for the initiation of treatment stimulation. Patients' treatment stimulation will not be delayed by participating in the study. Patients' medications will not be adjusted during the study. The study timeline is shown in Figure 1. Times are based on when surgery can be expected based on the decisions of the patient's surgeon and neurologist.

PROTOCOL TITLE: Safety and feasibility of using low frequency deep brain stimulation of the subthalamic nucleus to improve cognitive performance in patients with Parkinson's disease

[figure not shown]

Figure 1: Week 0 (W0): Pre-op visit, Baseline experimental cognitive testing (E-BL Cog) (may occur 1-2 wks prior to lead placement surgery), Week 1 (W1): Surgery 1: DBS lead placement surgery (S1 Lead) as scheduled by patients’ doctors, Week 2 (W2): Surgery 2: IPG surgery (S2 Battery) as scheduled by patients’ doctors, Week 3 (W3): Recovery, Week 4 (W4): Experimental testing sessions 1 (E1 Cog) and 2 (E2 Cog) with frequency modulation, check mark indicates telephone contact, Week 5 (W5): Treatment Stimulation typically turned on as part of routine care.

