Upon informed consent and enrollment, information regarding participants’ age, gender, medications, medical history, surgical history, disease duration and imaging (magnetic resonance imaging, computed tomography) will be collected. As part of the standard assessment prior to DBS electrode placement, all patients undergo evaluation with the Unified Parkinson’s Disease Rating Scale (UPDRS), Beck depression inventory (BDI) (Beck et al 1961), IQ testing, and a battery of neurocognitive tests. These tests are routinely repeated about 6 months to 1 year after DBS placement as part of patients’ routine care. These tests will not be a direct part of the study but may be utilized as part of the patient’s history.

As part of our experimental design, we will include a baseline experimental session prior to the patient’s planned surgery that will consist of approximately 30 minutes of cognitive testing and baseline screening for neuropsychiatric symptoms using the BDI and NPI (Cummings et al 1994). Cognitive testing will consist of computerized and non-computerized tests. The NPI requires that a caregiver answer questions about the mental state and behaviors of the patient. The caregiver will be informed of the study at the pre-op visit if the patient consents and will be asked if they are willing to participate in the study procedure.

After patients’ treatment team has performed their DBS surgeries, there will be two on-site experimental testing sessions with frequency manipulation and a telephone psychological screening session. The first will occur 22-24 days following the DBS lead placement surgery. During the session, each patient will repeat baseline cognitive testing

PROTOCOL TITLE: Safety and feasibility of using low frequency deep brain stimulation of the subthalamic nucleus to improve cognitive performance in patients with Parkinson's disease

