without stimulation and will complete the BDI. Informers will complete the NPI. Subsequently, the stimulators will be turned on, and each patient will repeat cognitive testing under gamma frequency (~130 Hz) and theta frequency stimulation (~5 Hz). The order of stimulation will be randomized. Stimulation will occur for 5 minutes prior to and continuously throughout each task. Amplitude and pulse width will be set to 3 V and 120 microseconds accordingly (Laxton & Lozano 2013) or as tolerated by the patient, and will remain constant across sessions. We will wait 20 minutes between testing conditions to elicit about 75% of DBS effects (Temperli et al 2003). At the end of the experimental testing session, the stimulator will be turned off or set to LFS in preparation for the second experimental session.

The second on-site experimental testing session will assess the effects of continuous theta stimulation on cognitive function. Patients will repeat cognitive testing after 48 hours of continuous theta stimulation. This second on-site testing session will occur 3-5 days following the first experimental session. Two days prior to the testing session, patients' stimulators will be turned on to the theta frequency stimulation setting and patients will return home and engage in normal activities. After 48 hours they will return to the clinic and repeat cognitive testing with continuous theta frequency stimulation. The UPDRS, NPI, and BDI will also be performed at this time. At the end of the session, their stimulators will be turned off.

We will screen for psychological changes by telephone once during the 2 day stimulation period. The patient will complete the BDI and a relative or caregiver will complete the NPI over the phone.

The structure of the experimental sessions is shown in Figure 2 and Figure 3.

[figure not shown]

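### Cognitive test blocks are neither matched to nor recorded against time since last dose, so the acute versus 48-hour low-frequency comparison can mix medication state with stimulation

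*Combined protocol and SAP*

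**What the plan says.** All references are to the Combined protocol and SAP.

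- **Medication handling (section 12, Procedures Involved).** Patients' "medications will not be adjusted during the study".
- **Medication data (section 12).** At enrolment the study collects age, gender and "medications, medical history, surgical history, disease duration and imaging". This is a single background record. The session procedures, the lists of stored data files (sections 14 and 29) and the analysis text (sections 14 and 15) mention no last-dose time, on/off state, clock time or dose-to-test interval.
- **Medication and cognition (section 5, Background).** Dopamine replacement "improves motor symptoms but shows mixed effects on cognitive symptoms".
- **Hypothesis (section 4, Objectives).** LFS will tend to improve performance, and "this improvement will be stable or enhanced with sustained LFS".
- **Acute LFS, in E1 (section 12).** "Stimulation will occur for 5 minutes prior to and continuously throughout each task". The order of high-frequency stimulation (HFS) and LFS is randomised; the no-stimulation block always comes first.
- **Sustained LFS, in E2 (section 12).** "Patients will repeat cognitive testing after 48 hours of continuous theta stimulation". Patients spend those two days at home in their usual activities.
- **Interval between sessions.** Section 12 says "This second on-site testing session will occur 3-5 days following the first experimental session". Section 10 gives 3-4 days. The Figure 2 caption starts LFS when E1 ends and runs it for 48 hours.
- **Analysis (section 14).** Stimulation settings are low, high and none. There is no sustained-LFS level and no medication term.

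**The concern.** An unchanged prescription does not mean an unchanged medication state at the moment of testing. The same patient could be tested soon after a dose in one session and late in the dosing interval in the other. Within E1 the randomised HFS/LFS order balances this on average between those two conditions. Nothing balances it between E1 and E2, because sustained LFS always comes later and on another day.

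At stake is the statement about durability. Section 11 says the results will help decide whether a large study is warranted, and section 4 says they will inform its design. If performance under sustained LFS differs from acute LFS, the team could not tell how much reflects 48 hours of stimulation and how much reflects when the last dose was taken. Dose times that are not recorded cannot be reliably recovered afterwards.

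**Working it through.** The plan states no power, alpha, effect size or SD, so there is no figure to reproduce. Section 7 says the study is not powered for efficacy.

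**Step 1. Where the LFS blocks fall.** From the Figure 2 caption, with 30 minutes per block (section 12), counting from the start of E1 cognitive testing:

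| Event | Minutes |
|---|---|
| No stimulation | 0–30 |
| Stimulation on | 30–35 |
| First frequency | 35–65 |
| Off, rest | 65–80 |
| Stimulation on | 80–85 |
| Second frequency | 85–115 |

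The total is 115 minutes. Section 12's block and gap times give 3×30 + 2×20 = 130 minutes. Both fit its approximate 2 hours. Acute LFS therefore starts at about minute 35 or 85, depending on randomised order (30+20 = 50 or 50+30+20 = 100 on the second tally). E2 has one cognitive block, with psychological screening after it, so sustained LFS starts at about minute 0.

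**Step 2. What the possible schedules imply for dose timing.**

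- *E1 and E2 testing started at the same time after a dose:* sustained LFS is tested 35 or 85 minutes earlier after the dose than acute LFS, in every patient. This creates a systematic difference.
- *Figure 2 version, exactly 48 hours from the end of E1:* the sustained block falls at the clock time of E1 minute 115, which is 115−35 = 80 or 115−85 = 30 minutes later in the day than the acute block. With a regular daily regimen this is a partial match.
- *Section 12 version, E2 at 3-5 days with LFS switched on two days before:* E2's time of day has no link to E1, so the difference is unrestricted.

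The no-stimulation block also precedes the stimulated blocks by 35 or 85 minutes, which is a reason to record dose time for every block.

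**Step 3. Illustrative size.** Assumptions not in the documents: paired t-test, n = 20, two-sided alpha 0.05, true change 0.5 SD of the within-patient difference. Power comes from the noncentral t distribution with 19 df and noncentrality d√20.

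Random timing noise of s SD reduces the effect to d = 0.5/√(1+s²):

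| s | d | Power |
|---|---|---|
| 0 | 0.500 | 56.5% |
| 0.3 | 0.5/√1.09 = 0.479 | 52.9% |
| 0.5 | 0.5/√1.25 = 0.447 | 47.6% |
| 0.8 | 0.5/√1.64 = 0.390 | 38.1% |

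A consistent shift with no true stimulation effect biases the contrast by its full size. The chance of a significant result is then:

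| Shift (SD) | Rejection rate |
|---|---|
| 0 | 5.0% |
| 0.1 | 7.1% |
| 0.2 | 13.6% |
| 0.3 | 24.7% |

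**The case against.** The case against is substantial, and much of it stands.

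- **The Background does not say that cognition varies within a dosing interval.** It describes dopamine replacement as a treatment that "shows mixed effects on cognitive symptoms, improving some, and worsening others". A reader might infer that the sponsor has conceded a time-since-dose effect; the text does not go that far. That the unadjusted medications are dopaminergic is also an inference, though a fair one, since the Background calls this the conventional therapy. Stands: the mechanism is plausible, not documented.
- **No acute-versus-sustained test is planned.** A reader might conclude that a prespecified analysis is biased. Section 14 contains no such analysis. Aim 3 concerns whether LFS-versus-HFS differences last; the comparison discussed here is required by the hypothesis in section 4. Stands. But a hypothesis without a specified analysis still needs usable data.
- **One version of the schedule already gives partial matching.** Stands for the Figure 2 version (30 or 80 minutes apart), not for the section 12 version.
- **The power figures are assumption only.** Stands. At s = 0.8, dose timing would be 0.64/1.64 = 39% of the variance of the difference, which nothing in the documents supports. The 0.3 case costs under 4 percentage points. An SD observed in medicated patients would already contain some timing noise, so adding more risks double counting. Nor does any passage show E2 falling consistently earlier or later after a dose.
- **It is a small feasibility study.** True, but its results are meant to guide a larger one.

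A stable regimen is not a full answer: it controls what is prescribed, not the state at testing.

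**Conclusion.** The gap is real and the point is minor. No test block is tied to, or recorded against, time since last dose, and the non-randomised E1-to-E2 comparison is the most exposed to this. Medication state can be mixed with duration of stimulation there; the direction and size are unknown, and the effect may be mostly noise. The figures above show what would follow under assumed inputs and do not estimate what will happen in this trial.

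The documents do not support saying that the durability result will be biased, or that the randomised HFS-versus-LFS comparison is systematically affected. What they do support is that, as planned, the team could neither rule out a dose-timing explanation nor adjust for one later.

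**What to change.** Leave medication unchanged and make these changes to conduct and reporting:

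1. Record the time of last dose before every test block: baseline, no stimulation, HFS, acute LFS and sustained LFS.
2. Book E2 so that the sustained-LFS block falls at about the same time since the patient's usual dose as that patient's acute-LFS block (about 35 or 85 minutes into E1 testing). Match the blocks, not the session starts: matching starts would introduce the systematic difference shown in the working. E1 will already have taken place, so the time to match is known.
3. Specify the acute-versus-sustained LFS contrast in section 14. Report it with the recorded dose times and a descriptive sensitivity analysis. State that adjustment for time since dose is imprecise at n = 20, and that matching does not remove practice effects.
4. Reconcile the E1–E2 interval across section 10 (3-4 days), section 12 (3-5 days) and the Figure 2 caption (48 hours from the end of E1). How closely the blocks can be matched depends on which applies.

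Cost: one case-report field per block and less flexible appointments; no extra visit or staff. This is a cheap improvement.

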Figure 2: Stimulation schedule. The first experimental session (E1) will include 30 minutes of baseline cognitive testing. Stimulation will then be turned on (Stim) for 5 minutes prior to cognitive testing under the first frequency condition (either HFS or LFS depending on randomization) (Cog C1). Stimulation will then be turned off and the patient will have a 15 minute rest period. Stimulation at the second testing frequency condition will then be turned on for 5 minutes and the cognitive testing will be repeated (Cog C2). At the completion of this session, LFS will be turned on for 48 hours. When the patient returns to clinic for the second experimental session (E2) they will repeat cognitive testing after sustained LFS (Cog S-Stim). The stimulation will be turned off and the patients will return home to continue standard care. Shaded boxes represent periods of stimulation.

PROTOCOL TITLE: Safety and feasibility of using low frequency deep brain stimulation of the subthalamic nucleus to improve cognitive performance in patients with Parkinson's disease

[figure not shown]

Figure 3: Safety Measures. Motor, psychological and cognitive tests present for each patient contact are indicated. *This motor test performed by neurologist as part of routine care and occurs at a clinic visit prior to the patient’s anticipated surgery.

We will also identify and enroll two subjects that have PD in order to test the ease of use of the computerized cognitive test, prior to the enrollment of additional subjects. These subjects will perform the computerized cognitive test once and will not participate in any other study procedures. We will use this information to decide on optimal parameters within the computerized cognitive test such as stimulus presentation time and response time allowed.

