We will also examine changes in psychological symptoms. For each individual patient, we will measure the BDI and NPI at baseline, at the first experimental session, by phone call after 24 h LFS, and at the final experimental session. For the BDI, we will consider any score greater or equal to 20 as evidence of moderate depression and will terminate the study for any individual that shows evidence of depression. At the group level, we will calculate

PROTOCOL TITLE: Safety and feasibility of using low frequency deep brain stimulation of the subthalamic nucleus to improve cognitive performance in patients with Parkinson's disease

the percentage of people that develop depression. For the NPI, we will calculate the total score. At the individual level we will look for the development of new symptoms in the 12 subsections. At the group level we will perform an ANOVA to look for significant changes across the 3 time points.

Cognitive Data Analysis:

The cognitive data analysis will examine the effect of theta frequency stimulation on cognitive task performance. Analyses for the Stroop task will include the examination of response time and error rates across stimulator settings. Two (trial type: congruent vs incongruent) by three (Setting: low, high, no stimulation) ANOVAs will be performed for both reaction time and accuracy. Post conflict and post error reaction time adjustments will also be examined across stimulator settings. For the N-back test, ANOVAs will also be performed to assess the effects of complexity (1,2-back) and stimulation frequency (none, high, low) on error rates. For the verbal fluency test, the average number of words generated across stimulation conditions and the change in word number on low and high frequency stimulation settings will be compared. Analyses will be performed using MATLAB and STATA.

Describe any procedures that will be used for quality control of collected data.

a.) Study-Wide:

NA

b.) Local

Describe the local procedures for maintenance of confidentiality.

This research is partly funded by a donation from the Chevo Foundation. The Chevo Foundation will not have access to any of the study documents including the data.

Data files to be stored include group assignment, background information, any head scans if performed, and results from neurocognitive and motor tests.

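### In experimental session 1 the unstimulated battery always comes first, so contrasts with no stimulation and the three-level Setting main effects are mixed with test order; low versus high frequency is protected on average from order, but not from carry-over.

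*Combined protocol and SAP*

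**What the plan says.** LFS is low (theta) and HFS high (gamma) frequency stimulation; E1 is the first experimental session.

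- **Order in E1 (section 12(a)).** "During the session, each patient will repeat baseline cognitive testing"; the sentence goes on to say that this is done without stimulation. Then: "Subsequently, the stimulators will be turned on, and each patient will repeat cognitive testing under gamma frequency" and theta frequency.
- **Randomisation.** "The order of stimulation will be randomized". Alone, this could be read as covering all three conditions. The Figure 2 caption settles it: "The first experimental session (E1) will include 30 minutes of baseline cognitive testing", and randomisation decides only whether HFS or LFS comes next.
- **Gap.** "We will wait 20 minutes between testing conditions to elicit about 75% of DBS effects". Figure 2 makes this up of 15 minutes off and 5 minutes at the new frequency.
- **Analysis (section 14, Cognitive Data Analysis).** Stroop: "Two (trial type: congruent vs incongruent) by three (Setting: low, high, no stimulation) ANOVAs will be performed for both reaction time and accuracy". N-back: "ANOVAs will also be performed to assess the effects of complexity (1,2-back) and stimulation frequency (none, high, low) on error rates". Verbal fluency: a comparison of "the average number of words generated across stimulation conditions", and of the changes under low and high frequency. No position, period or sequence term is planned.
- **Use of the results.** Aim 2 (section 4) looks for a trend to better executive function with LFS than with HFS and than with no stimulation. Section 11 uses the results to help judge whether a large study is warranted. Sections 11 and 15 also count cognitive change as safety data.

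**The concern.** No stimulation is always test 1; LFS and HFS always share tests 2 and 3. Anything that shifts scores between the first and later batteries of a long session enters every contrast with no stimulation. Practice is plausible, because the same three fluency letters recur in each battery. Fatigue is plausible too: the Figure 2 steps add up to 30 + 5 + 30 + 15 + 5 + 30 = 115 minutes.

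Two uses of the data are exposed. For aim 2, upward drift can look like a stimulation benefit and downward drift can hide one. For aim 1, upward drift can mask a real cognitive worsening relative to no stimulation. A larger sample would not cure either, since this is bias and not imprecision.

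**Working it through.** The plan gives no effect size, SD, alpha or power, so it has no figure to reproduce.

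**Inputs.** From the documents: 20 analysed patients (22 less 2 ease-of-use subjects) and orders none-LFS-HFS or none-HFS-LFS. Assumed: 5% two-sided tests; residual SD of 1 per test occasion; simple randomisation of the order; drift of d SD per position, so shifts of 0, d and 2d.

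**1. Estimability.** The model patient + setting + position has 20 + 2 + 2 = 24 columns but rank 23, because the LFS and HFS indicators add up to the position 2 and 3 indicators. LFS-none and HFS-none are not estimable; LFS-HFS is.

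**2. Bias.** With position shifts p2 and p3, LFS-none carries (p2 + p3)/2 on average. Under linear drift this is (d + 2d)/2 = 1.5d. LFS-HFS carries zero on average.

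**3. False findings with no true effect** (simulation of the one-way layout):

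| d | Setting, nominal 5% | LFS better than none, nominal 2.5% | LFS beats both none and HFS |
|---|---|---|---|
| 0.1 | 7% | 7% | 0.8% |
| 0.2 | 14% | 14% | 1.3% |
| 0.3 | 27% | 27% | 1.7% |
| 0.4 | 44% | 43% | 2.1% |

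The third column can be checked by hand. At d = 0.2 the noncentrality is 1.5 × 0.2 / √((2 + 0.2²/4)/20) = 0.30/0.317 = 0.95 on 19 df, which gives 14.4%. Negative drift gives the same Setting rates. LFS-versus-HFS stays at 4.7 to 5.2% throughout.

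**4. Stroop 2 × 3.** If drift is common to both trial types and half the occasion variance is shared between them, the false Setting main effect is 8 / 17 / 34 / 56%. The interaction stays near 5%. If congruent trials drift at half the rate, the interaction reaches 13.6% at d = 0.4.

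**5. If HFS does harm and LFS does nothing.** Sections 5 and 12 say that DBS may impair these tests. With an assumed HFS harm of 0.5 or 1 SD, LFS beats HFS (period-adjusted, one-sided 2.5%) in about 31% or 83% of trials at every drift. A false finding that LFS beats both then occurs in about 4 / 9 / 15 / 20% (0.5 SD) or 6 / 14 / 26 / 40% (1 SD) at d = 0.1 to 0.4.

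**6. Safety.** If LFS and HFS both worsen cognition by 1 SD, LFS-versus-none detects it in 85% of trials without drift, but in 72 / 55 / 37 / 22% at d = +0.1 to +0.4. LFS-versus-HFS shows only its nominal 5%.

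**7. Linear-drift correction.** Subtracting 1.5 times the third-minus-second difference makes LFS-none estimable, with SE √(2/20 + 1.5² × 2/20) = √0.325 = 0.570 against √(2/20) = 0.316. It depends on the straight line: with shifts of 0 / 0.5 / 0.5 the correction averages zero, the bias of 0.5 SD remains, and the false Setting rate is 33%.

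**8. Carry-over.** Read the 75% figure as leaving a quarter r = 0.25 of the first frequency's effect at the second test, for both frequencies. With balanced order, the expected LFS-HFS is (L + 0.125H) − (H + 0.125L) = 0.875(L − H). A true 0.50 is estimated as 0.4375, and a true zero stays zero. If the residual fractions differ, a bias of (r_H × H − r_L × L)/2 arises.

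**The case against.** **Phase 1, not powered for efficacy.** Section 7 says so, aim 2 seeks only a trend, and there is no formal go/no-go rule. This limits the stakes and makes the point one of analysis and reporting. It does not remove the bias, which a descriptive estimate carried into a phase 2 design would inherit.

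**Drift is assumed.** True: size and sign are unknown, and the rates are illustrations. The pre-operative battery and the Stroop key-press training may put practice at the low end. They do not remove drift within E1, and using the pre-operative battery as the unstimulated level would add surgery and elapsed time to the confounding.

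**Safety does not rest on one test at n = 20.** Section 15 has data reviewed after each contact and by the committee after 4, 8, 12 and 20 patients. The power figures in step 6 therefore show direction and scale, not the performance of the monitoring. Those reviews do see cognitive data collected in the same fixed order.

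**Stronger readings that the documents do not support.**
- A reader might infer that contrasts with no stimulation can never be recovered. That holds for unrestricted position effects; a straight-line assumption recovers them, at the cost in step 7.
- A reader might infer that the whole cognitive analysis fails. It does not: LFS-HFS is sound against order. So is the comparison of LFS and HFS fluency changes if both are taken from the same unstimulated test, since it reduces to LFS-HFS.
- A reader might infer that LFS-HFS is clean in every respect, or that requiring LFS to beat both comparators guards against drift. The first ignores the short gap. The second holds only if HFS has no effect.

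**Conclusion.** The point stands as a should-fix. The fixed first place of the unstimulated battery is explicit, and the planned ANOVAs ignore it. Taken alone, a Setting main effect for Stroop or N-back, or a fluency comparison that includes no stimulation, cannot be attributed to stimulation. At assumed drifts of 0.1 to 0.4 SD per position the false Setting rate runs from about 7% to 44%, while LFS-HFS keeps its level. The non-estimability follows from the design; the rates rest on 20 patients, unit residual SD and linear drift.

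Two limits belong with this conclusion. LFS-HFS is protected on average against position effects, but carry-over can attenuate it, by 12.5% on the reading in step 8. And it answers a narrower question: LFS better than HFS is a difference between frequencies, not by itself evidence that LFS improves cognition over no stimulation.

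**What to change.** Change the analysis wording in section 14, and the reading of aim 2:

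1. Analyse LFS minus HFS in E1 in a within-patient model with setting and period (second or third test), plus trial type for Stroop or load for N-back.
2. Report LFS-none, HFS-none, the three-level Setting main effects and any fluency comparison that includes no stimulation as descriptive, labelled *confounded with test order*. Do not use them alone to support a larger trial. If the three-level Stroop interaction is reported, say that it assumes equal drift for both trial types.
3. State that LFS better than HFS may reflect impairment under HFS.
4. Keep cognitive change from no stimulation in the safety review, noting that drift can bias it in either direction. LFS-HFS does not replace it.
5. Do not use the third-minus-second difference as evidence that drift is absent.

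A design alternative should be named for the investigators to weigh; it is not a required change. Including no stimulation in the randomised order (six orders), with a position term, makes LFS-none estimable at SE 0.317 against 0.316 residual SD, with no extra tests. It exposes the unstimulated test to carry-over, which the present order avoids.

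Cost of items 1 to 5: one model term and revised wording, with no extra visits, tests or patients. The downside is that there is no inferential efficacy claim against no stimulation, so that half of aim 2 is answered only descriptively unless the order is changed.
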